3. STUDY DESIGN

This study is designed as a single center pilot study. The aim of this study is to assess the role of left atrial fibrosis and its characteristics prior to and after mitral valve repair surgery in MVI patients.

Study subjects that will be included are MVI patients who meet the criteria for mitral valve repair surgery and are on the waiting list for elective surgery. Exclusion criteria are: AF, history of cardiac surgery, comorbidities, MRI contra-indications. The study subjects are recruited from the Amsterdam UMC surgical waiting list.

The study subjects will visit the AmsterdamUMC hospital (Location VUmc) two weeks prior to mitral valve repair surgery for a CMR scan. This visit will start with checking in- and exclusion criteria using questionnaires regarding medical history and MRI safety. The total duration of the visit, including the CMR scan, will be approximately two hours.

[figure not shown]
Two weeks later the subjects will undergo mitral valve repair surgery (Location AMC). During anesthesia, a Swan-Ganz catheter will be used for hemodynamic monitoring. This Swan-Ganz catheter is part of the standard care for mitral valve repair surgery.

At three months follow-up, subjects will visit the AmsterdamUMC hospital (Location VUmc) for a second CMR scan to assess reversed atrial remodeling and amount of fibrosis.

Image data from age and gender matched controls will be retrieved from an existing database. The patients in this database have undergone the same MRI scan protocol (for a different medical indication) as scheduled for our study population. Only data from patients without MVI and AF will be used from the database for reference. Absence of MVI and AF will be confirmed by checking ECGs and echocardiography of the control patients.

See *figure 2* for a schematic representation of the study design.

Figure 2. Schematic representation of the study design: Left atrial remodeling in MVI

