2. OBJECTIVES

Primary Objective:

To assess

- the effects of (reduced) volume overload on the left atrial wall texture (presence, amount and location of atrial fibrosis) and associated geometry and function in patients with MVI, prior to and after elective mitral valve repair surgery.

Secondary Objectives:

To assess;

- the value of LA fibrosis in stratification and timing of mitral valve repair surgery.
- the impact of atrial fibrosis on myocyte contractile function (atrial strain, quantified by CMR).
- whether left ventricular (LV) volume overload results in increased extra cellular volume (ECV) and whether this is reversible after mitral valve repair surgery.
- the impact of LA remodeling on right atrial (RA) function and tissue characteristics.
- the predictive value of LA fibrosis for outcomes of AF and atrial function during post-surgical follow up

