4. STUDY POPULATION

4.1 Population (base)

The research population consists of MVI patients scheduled for elective surgical mitral valve repair conform the current guideline criteria.

These patients will be recruited from the surgery-waiting list / database of the AUMC after they have been accepted for surgery by a multidisciplinary heart team.

Data from a control group of non-MVI/AF age-sex matched controls (N=10) will be retrieved from an existing database. These controls have undergone the same MRI scan protocol for a different medical indication.

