4.3 Exclusion criteria

Patients that will be excluded from our study are patients;

- not able to provide written informed consent.
- under the age of 18.
- with a history of cardiac surgery
- with AF
- with any comorbidity besides MVI.
- with claustrophobia or any other contra-indication for MRI
 - Each participant will be requested to fill out the “Questionnaire for MRI research with human volunteers” (“*Vragenlijst voor MRI-onderzoek bij testpersonen*”). This standard MRI safety document that is required to be filled in by anybody undergoing MRI scanning contains (among other items) questions on whether

or not the participant has ever had any surgical procedures, has any (metallic) implants or has any other metallic parts in his/her body e.g. splinters.

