In the occurrence of a clinical relevant incidental finding patients will be informed by their treating physician. During the informed consent patients will be notified of this obligation. Patients who refuse to be informed about clinical relevant incidental MRI findings, will be excluded from this study.

MRI processing

Quantification of LA fibrosis will be performed using commercially available ADAS 3D LA image post-processing software (Galgo Medical, Barcelona, Spain) and open-source CEMRG image post-processing software (King's College London, United Kingdom). The 3D LGE images will undergo stringent quality control (i.e. artefacts, proper myocardial nulling) by two experienced readers prior to post-processing and images will be excluded from analysis if quality is deemed insufficient.

[figure not shown]

Figure 3. Left atrial 3D reconstruction from MRI.

Left Atrial remodeling

LA remodeling will be assessed by quantifying atrial sphericity and calculation of the wall tension calculation using Laplace's law ($T = p \times r / 2T$). This calculation includes pulmonary wedge pressure which is determined using peri-operative Swan-Ganz based pressure measurements during anesthesia, and radius based on atrial volume and wall thickness. Also the relation to quantitative MVI will be determined using 4D-flow MRI processing.

Presence and distribution of LA fibrosis

Quantification of fibrosis surface and the distribution of fibrosis will be assessed using LA 3D reconstructions based on 3D MRA data. Output of this data will be as shown below in Figure 4. The left atrial wall is segmented for accurate geometric localization of fibrosis (*Figure 4A*) and the severity of fibrosis will be shown as quantified surface area (*Figure 4B*).

[figure not shown]

Figure 4. Left atrial segmentation (A) for accurate assessment of geometric distribution of fibrosis and severity of fibrosis shown as quantified surface (B).

4D Flow

4D-flow data will be corrected for Maxwell terms in the image reconstruction at the scanner, and velocity aliasing during post-processing. 4D flow data will be co-registered with the cine images to guide left atrial anatomic orientation. Mean and peak flow velocity data will be derived using dedicated research software (MASS version 2017-Exp, Leiden University Medical Center, Leiden, the Netherlands). Furthermore, the volume fraction in the left atrium with a flow velocity below 10cm/s during the entire cardiac cycle will be determined.

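### Scar from the study operation can appear only on the second scan, and nothing in the plan separates it from the fibrosis change attributed to reduced volume overload

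*Combined protocol and SAP*

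**What the plan says.** Section 3 has patients attend "two weeks prior to mitral valve repair surgery for a CMR scan" and return at three months "for a second CMR scan to assess reversed atrial remodeling and amount of fibrosis". Between the two visits every patient is due to have the operation; section 4.1 describes the participants as "MVI patients scheduled for elective surgical mitral valve repair conform the current guideline criteria". The surgical approach and any atrial incision are not described.

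Section 2 states the primary objective as assessing "the effects of (reduced) volume overload on the left atrial wall texture", and specifies the presence, amount and location of fibrosis. Section 5.1.1 lists fibrosis surface and its geometric distribution among the main parameters. The Summary and section 1 hypothesise that fibrosis surface area will rise after surgery because the atrium shrinks.

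Section 5.2 names two software packages and allows images to be dropped for poor quality (artefacts, nulling). It adds: "The left atrial wall is segmented for accurate geometric localization of fibrosis". It gives no enhancement threshold, no scar category, no masked region and no analysis that leaves out operated wall. Section 7.1 contains no adjustment for scar. The 10 database controls are selected for absence of MVI and AF and serve as reference.

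**The concern.** The before/after contrast carries two things at once: the relief of volume overload, and the operation that delivers it. If the operation leaves enhancing scar in the atrial wall, that scar is absent from the first scan and present on the second, so it does not cancel. It would raise the fibrosis total, which is the direction of the stated hypothesis, and it would shape the distribution map around the operated sites.

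Section 1 suggests that surgery might be withheld where a substantial postoperative increase in fibrosis is expected. An increase produced partly by the operation's own scar could be taken as evidence of adverse remodelling and carried into that argument, and into any larger study built on this pilot.

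**Working it through.** The plan gives no effect size, standard deviation or power, so there is no figure to reproduce. The core check is a reading of the text; the arithmetic only shows whether the bias could matter.

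**1. Can scar cancel between the scans?** Section 4.3 excludes patients "with a history of cardiac surgery", so preoperative scans should carry no scar from earlier heart surgery. Scar from the study operation can be present only at three months. It does not cancel.

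**2. Does any planned element separate it?**
- Image exclusion (5.2) is for quality only.
- Segmentation (5.2) is for localisation; no rule uses the segments to set operated wall apart.
- Controls (3, 4.1) are database images used for reference. No operated comparison group is planned.
- The relation to quantitative MVI (5.2) sits under LA remodelling, with sphericity and wall tension, and does not explicitly extend to fibrosis.
- Correlation analyses (7.1) are named in general terms only.

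None separates scar from remodelling fibrosis.

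**3. Scale, first set of assumptions.** Scar line 8-10 cm long and 0.5-1.0 cm wide; wall 150 cm².
- 8 × 0.5 = 4 cm²; 4/150 = 2.7 points.
- 10 × 1.0 = 10 cm²; 10/150 = 6.7 points.

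**4. Scale, second set of assumptions.** Spherical atrium of 100-150 mL, shrinking by 20-40%; fibrosis area fixed at 10% of the preoperative wall; scar 2-8 cm². Wall area A = 4π(3V/4π)^(2/3).
- Preoperative wall: 104.2 cm² (100 mL) and 136.5 cm² (150 mL).
- Postoperative wall: from 74.1 cm² (100 mL, 40% shrinkage) to 117.7 cm² (150 mL, 20% shrinkage).
- Shrinkage alone multiplies the fibrosis share by (1 − shrinkage)^(−2/3), that is 1.160 to 1.406, so 10% becomes 11.6% to 14.1%: +1.6 to +4.1 points.
- Scar adds 2/117.7 = 1.7 points up to 8/74.1 = 10.8 points.

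Together the two sets span roughly 2 to 11 points. Pairing the largest scar of the first set with the smallest wall of the second would give 10/74.1 = 13.5 points.

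**5. The unit matters.** Under the fixed-fibrosis assumption in step 4, shrinkage raises fibrosis as a share of the wall and leaves its absolute area unchanged. Section 5.1.1 does not say whether fibrosis surface is analysed in cm² or as a percentage. In cm², scar would move the endpoint while shrinkage alone would not.

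**6. Effect on a test.** Section 7.1 names no paired test, so assume a two-sided paired t-test at 0.05 with n = 20 and no true change. If scar shifts the mean by d standard deviations of the paired differences, the noncentrality is d√20 on 19 degrees of freedom:

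| d | Probability of p < 0.05 |
|---|---|
| 0.25 | 0.19 |
| 0.50 | 0.56 |
| 0.75 | 0.89 |
| 1.00 | 0.99 |

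The nominal rate is 0.05. The documents give no basis for choosing d.

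**7. Could the change in regurgitation settle attribution?** With n = 20, 80% power and two-sided 0.05, Fisher's z must reach (1.960 + 0.842)/√17 = 0.679, and tanh(0.679) = 0.59. Only a correlation of about 0.59 or more is detectable at that power.

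**The case against.** The strongest reply is that the mechanism is not in the documents. They do not call the surgery open or describe an incision. That the repair scars the atrial wall, and that late enhancement does not separate such scar from remodelling fibrosis, is outside inference. This stands: both must be labelled as inference, and the size of the bias is unknown.

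A reader might infer that the plan counts all atrial enhancement as fibrosis. The text does not say so; it is silent on thresholds and classification. What can be said is that no separating rule is prespecified.

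A reader might also see a contradiction between excluding earlier cardiac surgery and scanning after the study operation. There is none. The exclusion keeps the first scan free of earlier scar; its relevance is only that scar from the study operation then appears on one side of the contrast. Nor do the documents show the three-month timing itself to be a fault.

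Patients with residual regurgitation are not ignored: regurgitation volume is a main parameter at both times. Concomitant atrial procedures may be less likely, since AF and any comorbidity besides MVI are exclusions, but they are not ruled out.

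Finally, this is a 20-patient pilot with no confirmatory rule, and regional results could still be drawn from the same images. That limits the claims that may follow. It does not remove a bias with a known direction, and choosing regions after seeing the postoperative images would be open to selection.

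**Conclusion.** The point holds. As written, the main fibrosis contrast cannot distinguish unloading from the operation, and any scar would act in the hypothesised direction on both amount and location. This should be corrected before postoperative images are read, because following the plan would give a biased primary contrast.

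The conclusion rests on one inference: that the repair leaves some enhancing scar in the atrial wall. The range of roughly 2 to 11 percentage points is an illustration on assumed scar and wall areas. It shows that scar could match or exceed the assumed shrinkage effect. It does not show that it will, nor that an observed increase would be scar alone.

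**What to change.** In section 5.2, before any postoperative image is read:

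- Prespecify the LA segments at the surgical access site and at any concomitant atrial procedure, both taken from the operation note, and a peri-annular band of stated width.
- Exclude the same regions from both scans. Make fibrosis in the remaining wall the main before/after comparison, and report whole-LA and surgical-region fibrosis separately as secondary.
- State whether fibrosis is analysed in cm² or as a percentage of wall.
- Word the conclusion as change following mitral valve repair, not as an effect of reduced volume overload alone.
- Report the relation between fibrosis change and change in regurgitation volume as supportive and exploratory. It should not be a condition for attribution: besides the limited power, an unloading effect of similar size in every patient would produce little correlation.

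The cost is protocol wording and a few operation-note fields, with no extra scan. Some wall drops out of the main comparison, so true fibrosis there is not counted in it, and the surgical regions must be mapped by hand onto the preoperative scan of an atrium expected to change size.

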4. STUDY POPULATION

4.1 Population (base)

The research population consists of MVI patients scheduled for elective surgical mitral valve repair conform the current guideline criteria.

These patients will be recruited from the surgery-waiting list / database of the AUMC after they have been accepted for surgery by a multidisciplinary heart team.

Data from a control group of non-MVI/AF age-sex matched controls (N=10) will be retrieved from an existing database. These controls have undergone the same MRI scan protocol for a different medical indication.

4.2 Inclusion criteria

The following patients will be targeted for inclusion.

- Patients that meet the criteria for elective mitral valve repair surgery according to the European clinical guidelines (class I recommendation);
 - Symptomatic, chronic severe mitral valve insufficiency due to degenerative valve disease with a left ventricular ejection fraction (LVEF) >30%.
 - Asymptomatic, chronic severe mitral valve insufficiency due to degenerative valve disease with a LVEF <60% and/or a left ventricular end-systolic diameter (LVESD) >45 mm.

4.3 Exclusion criteria

Patients that will be excluded from our study are patients;

- not able to provide written informed consent.
- under the age of 18.
- with a history of cardiac surgery
- with AF
- with any comorbidity besides MVI.
- with claustrophobia or any other contra-indication for MRI
 - Each participant will be requested to fill out the “Questionnaire for MRI research with human volunteers” (“*Vragenlijst voor MRI-onderzoek bij testpersonen*”). This standard MRI safety document that is required to be filled in by anybody undergoing MRI scanning contains (among other items) questions on whether

or not the participant has ever had any surgical procedures, has any (metallic) implants or has any other metallic parts in his/her body e.g. splinters.

4.4 Sample size calculation

This study is designed as a pilot study, since we are the first to assess the effect of LA fibrosis and its characteristics prior to and after mitral valve repair surgery.

Therefore we aim to include;

- 20 patients with MVI which are admitted to mitral valve repair surgery

5. METHODS

5.1 Study parameters/endpoints

5.1.1 Main study parameter/endpoint

The main study parameters are:

1. Severity of MVI prior to and after surgery (defined as regurgitation volume in ml)
2. Left atrial remodelling prior to and after surgery
 - Left atrial volume
 - Calculated left atrial sphericity
 - Estimated wall tension (wall thickness, radius, pulmonary wedge pressure)
 - Mitral regurgitation flow measurement (quantitative)
3. Presence and distribution patterns of LA fibrosis
 - Quantification of fibrosis surface (severity)
 - Geometric distribution of fibrosis (localization)
4. Blood flow patterns in the LA (4D Flow)
 - Flow velocity (mean and peak)
 - Static fraction
 - Kinetic energy

Secondary study parameters/endpoints -Fibrosis associated biomarkers derived from blood samples (NT-proBNP, TNF- β , Angiotensin II, cytokines)

-Heart failure symptoms monitoring derived from questionnaire preoperative and at postoperative follow-up

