5.1.2 Other study parameters

The following parameters will be recorded for each participant:

- Clinical routine Cardiac MRI parameters (global volumes and function, T1 maps, ventricular fibrosis (LGE))
- Anthropometric data; height, weight
- Clinical information potentially relevant to the study; medical history and medication use

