7. STATISTICAL ANALYSIS

7.1 Primary study parameters

CMR qualitative and quantitative analyses will be performed on a dedicated work-station with counseling of investigators experienced in the post-processing of CMR techniques.

The included data will be presented as mean \pm standard deviation. Ratios will be given for statistical assessment of non-continuous variables. Correlation analyses will be used to analyze differences between continuous parameters. Confidence intervals (95%) will be used and a $p < 0.05$ will be considered statistically significant. Fisher exact test will be performed to verify significance, risk ratio (RR) and 95% confidence intervals. SPSS 26.0 (SPSS Inc, Chicago, IL) for Windows is used to assess statistical analyses.

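### Unadjusted correlations across 20 patients between absolute regurgitation volume and unindexed LA volume can be inflated by body size, although height and weight are already recorded

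*Combined protocol and SAP*

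**What the plan says.** All places are in the combined protocol and SAP.

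- **Severity of insufficiency (5.1.1):** "Severity of MVI prior to and after surgery (defined as regurgitation volume in ml". This is the only main parameter listed with an absolute unit.
- **LA size (5.1.1):** "Left atrial volume" stands under LA remodelling with no unit and no index.
- **Fibrosis (5.2):** "the severity of fibrosis will be shown as quantified surface area". Whether this is an absolute area or a share of the wall is not stated.
- **Association (5.2, Left Atrial remodeling):** "Also the relation to quantitative MVI will be determined using 4D-flow MRI processing".
- **Method (7.1):** "Correlation analyses will be used to analyze differences between continuous parameters", with significance at p<0.05. No covariate is named.
- **Body size (5.1.2):** "Anthropometric data; height, weight" are recorded for each participant. Section 7 gives them no part in the analysis of the main parameters, and body surface area is not mentioned anywhere.
- **Controls (4.1):** "Data from a control group of non-MVI/AF age-sex matched controls (N=10) will be retrieved from an existing database". The Summary gives their purpose as reference.
- **Primary objective (section 2):** the state of the left atrium before and after surgery in the operated patients.

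**The concern.** A correlation across 20 people mixes every reason why two measurements rise together. A larger person can be expected to have a larger atrium and, for the same grade of valve disease, a larger regurgitant volume in ml. Without adjustment, part of any positive correlation between the two may reflect stature and weight rather than the effect of volume overload on the atrium, which is what the study wants to learn about.

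The same applies to fibrosis if it is measured as an absolute area. There a second mechanism is at work: a larger atrium has more wall, so more square centimetres can be fibrotic at the same fibrotic fraction.

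At stake is the reading of the exploratory associations. A pilot's correlations may inform later work, and here they would come with p-values whose real error rate exceeds the nominal 5%. The reference controls raise a milder form of the problem: they are matched on age and sex but not on size, so unindexed volumes set beside each other carry any difference in body size.

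**Working it through.** The plan gives no effect size, standard deviation or power to reproduce; section 4.4 justifies 20 patients by pilot status alone. Inputs from the documents are N=20 patients, 10 controls and significance at 0.05 (two-sided assumed). Every variance share and scaling figure below is an assumption.

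**1. Induced correlation.** Let each of two parameters owe a share s of its variance to body size, with no other link. Each then correlates √s with size, and the two correlate r = √s × √s = s. Shares of 10%, 20% and 30% give r = 0.10, 0.20 and 0.30.

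**2. False-positive rate.** The critical value at N=20 is |r| = t/√(18 + t²) with t = 2.101 on 18 df, that is 2.101/√22.41 = 0.444. Simulating 1,000,000 samples of 20 per setting:

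| Share of variance due to size | Induced r | Plain correlation, p<0.05 | Partial correlation given BSA |
|---|---|---|---|
| 10% | 0.10 | 7.0% | 5.0% |
| 20% | 0.20 | 13.5% | 5.0% |
| 30% | 0.30 | 25.4% | 5.0% |

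**3. Cross-check on a scaling model.** Let each parameter scale as BSA to the power b. Let BSA have log-SD sB and let the remaining log-SD be s. Then r = b²sB²/(b²sB² + s²). Central values are sB = 0.12 and s = 0.30.

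- b = 1: 0.0144/(0.0144 + 0.09) = 0.14, false-positive rate 9%.
- b = 1.5: 0.0324/(0.0324 + 0.09) = 0.26, false-positive rate 20%.

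Over sB 0.10 to 0.15, s 0.15 to 0.40 and b 1 or 1.5, the range runs from r = 0.06 (about 5.5%) to an extreme corner of r = 0.69 (95%). The partial correlation stays at about 5% throughout (0.046 to 0.055). Correlating two BSA-indexed ratios gives about 5% when b = 1 but up to 13% when b = 1.5, so the partial correlation is the safer choice.

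**4. Fibrosis area against LA volume.** If fibrosis is an absolute area and the fibrotic fraction is unrelated to LA volume, wall area scales as volume to the power 2/3. With log-SD 0.2 or 0.3 for volume and 0.3 or 0.5 for the fraction, geometry alone gives r = 0.26 to 0.55 and false-positive rates of 19% to 76%. Example: (2/3 × 0.2)/√(0.133² + 0.5²) = 0.133/0.517 = 0.26. This is as large as or larger than the central body-size effect in step 3, and BSA adjustment does not remove it.

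**5. Patients beside controls (20 and 10), sB = 0.12.** With no systematic BSA difference there is no average bias. A chance imbalance of exp(1.96 × 0.12 × √(1/20 + 1/10)) − 1 = 9.5% is still within the 95% range. A true difference of 0.10 log units would shift unindexed values by exp(0.10b) − 1, that is 10.5% for b = 1 and 16.2% for b = 1.5. If age and sex explain 10%, 20% or 30% of the variance, including them multiplies the CI width by √(1 − R²) × t(26 df)/t(28 df) = 0.95, 0.90 or 0.84.

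**The case against.** The strongest reply is that the primary contrast is before against after surgery in the same patients. Body size largely cancels there if weight is stable. That stands, and it limits the point to associations across patients and to the control reference.

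Several stronger readings are tempting, but the documents do not support them:

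- **That the main parameters as a whole are absolute volumes or areas.** Sphericity is a shape measure and velocity is neither volume nor area. The static fraction is defined as a share: "the volume fraction in the left atrium with a flow velocity below 10cm/s during the entire cardiac cycle will be determined".
- **That fibrosis is planned as an absolute area.** The hypothesis that fibrosis surface rises because the atrium shrinks reads more naturally as a share of the wall. The measure is undefined rather than clearly absolute.
- **That wall tension is affected through its radius.** It uses radius over wall thickness, so size largely cancels if both scale with the body.
- **That a biased test against controls is planned.** No such test is specified; the controls serve as reference.
- **That 10 controls for 20 patients breaks the matching.** One-to-one matching is never promised, and group matching is compatible with these numbers.

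It can also be said that the paragraph relating remodelling to insufficiency in section 5.2 speaks of sphericity and wall tension, with LA volume entering only through the radius. But section 5.1.1 lists LA volume under remodelling, so the volume-to-volume correlation is within the plan. A correlation of LA volume with fibrosis surface is not named; it is only possible under the general wording of section 7.1.

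Finally, the induced r of 0.10 to 0.30 lies below the critical 0.444, so size alone would usually not reach significance. That is true, but it still inflates the estimate and raises the error rate.

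**Conclusion.** The point holds in a limited form. For between-patient correlations of absolute volumes, above all regurgitation volume with LA volume, the planned unadjusted analysis can overstate the association. If size explains 10% to 30% of each variance, r is inflated by 0.10 to 0.30 and the false-positive rate is about 7% to 25% instead of 5%. These shares are assumed, so the size of the effect is uncertain; that no adjustment for body size is planned is plain from the text. Fibrosis is included only if it turns out to be an absolute area.

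A reader might infer that the before-after results are compromised. They are not. The weight is that of a worthwhile, cheap improvement to exploratory analyses in a pilot, using measurements already collected.

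**What to change.** Amend section 7.1 as follows.

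1. State the unit of each main parameter, including whether fibrosis surface is an area or a percentage.
2. Compute BSA from the recorded height and weight. Report between-patient correlations of absolute volumes, and of fibrosis area if absolute, as partial correlations given BSA with 95% CI. Do not correlate two BSA-indexed ratios.
3. Report fibrosis also as a percentage of LA surface, because BSA adjustment leaves the geometric link with LA volume in place.
4. Where patients are set beside the controls, show BSA-indexed LA volume if control height and weight can be retrieved. Describe any difference by a 95% CI from a linear model with age and sex.
5. Keep absolute values for the before-after change.

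The cost is SAP wording, one degree of freedom for each correlation (18 to 17 with 20 patients) and two for the control comparison (28 to 26). The documents do not say whether height and weight exist for the database controls; any control without them drops out of the indexed display. No new visit or procedure is needed for the patients.
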